### 2.2 General Considerations Impacting the Data Analysis

- This Statistical Analysis Plan (SAP) is based on Clinical Trial Protocol 2018-10 Version 2.0 dated October 16, 2018.

- All calculations will be performed using Statistical Analysis Software (SAS 9.2 and JMP Version 12 or higher both from SAS Institute, Cary, NC).
- The enrollment target is 731 non-advanced neoplasia and negative evaluable subjects with the maximum enrollment to be set at approximately 942 subjects to account for subject discontinuation.
- This study will be performed at approximately 35 clinical sites to be pooled for analysis; no individual sites will be analyzed separately.
- Analyses will be conducted at the subject level with the most clinically significant lesion category used for analyses when multiple lesions are found during colonoscopy.
- Final analyses will be conducted after the last subject completes their colonoscopy or discontinues the study.
- Effectiveness analyses include a primary endpoint and all other defined exploratory endpoints for Intent-to-Screen (ITS) population.
- One-sided  $p=0.025$  or two-sided  $p=0.05$  will be required to achieve statistical significance; no  $p$ -value adjustment will be made for testing multiple effectiveness endpoints.
- This analysis may be used to support use of Cologuard tests in subjects 45-49 years of age.
- There is 1 primary endpoint
- There are additional exploratory endpoints of interest (see Section 2.8.1).
- The effect of early withdrawals will be assessed using sensitivity analyses for just the primary effectiveness endpoint.
- All effectiveness analyses will be performed using the ITS Population with confirmation in a Per Protocol (PP) Population.

### 2.3 Study Objective

The study objective is to confirm the specificity of the multi-target stool DNA (mt-sDNA), Cologuard, test in an average risk population, ages 45-49.

### 2.4 Lesion Classification

A colonoscopy that was limited in any way but wherein a colorectal cancer or advanced adenoma was identified or wherein a partially obstructing colorectal cancer or advanced adenoma was identified will be included in the analyses. Colonoscopic findings will be recorded on the colonoscopy reports per site-specific standard of practice. Histopathology interpretation of tissue samples will be conducted according to standard practice of each clinical site.

Lesion classification is based on the most significant lesion. The location within the colorectum (site) and size (mm) is recorded for all index lesions. TNM stage and overall CRC Stage (I-IV) will be recorded for all CRCs. If a subject has CRC(s), the subject will be classified as category (1.0) regardless of the presence of any other adenomas or hyperplastic polyps. In the presence of multiple (synchronous) CRCs, a subject will be classified by the most advanced CRC stage.

Similarly, in the absence of CRC, a subject with AA will be categorized as category (2.0) regardless of the presence of any other adenomas or hyperplastic polyps. With category (2.0), subjects will be categorized by the most clinically significant AA subcategory. For this study, the hierarchy of clinical significance in descending order of significance is Subcategory 2.1 (highest clinical significance), then Subcategory 2.2, then Subcategory 2.3, and then Subcategory 2.4 (lowest clinical significance). In summary, subjects will

be placed in the lowest applicable Subcategory for this study, based on the most clinically significant lesion confirmed on histopathologic analysis. The presence of multiple advanced adenomas will not change the classification of a subject as category 2.0. The most clinically significant lesion is hereafter referred to as the index lesion and is the lesion upon which the subject categorization will be made.

Subjects with pathologically confirmed non-advanced adenoma(s) but without CRC (1.0) or advanced adenoma (2.0), subjects will be classified by the reviewing pathologists into category 3.0, 4.0, or 5.0 based on the size and number of lesions. The largest of the non-advanced adenomas will be the index lesion for the case. In the scenario a subject has both small (<10 mm) non-advanced adenomas and hyperplastic polyps < 10mm, the subject will be classified based on the non-advanced adenoma(s) only and will be classified into category 3.0, 4.0, or 5.0.

All subjects who do not have CRC (1.0), advanced adenoma (2.0), small or non-advanced adenomas (3.0, 4.0, or 5.0) will be classified as negative (6.0). Category (6.0) includes subjects with any number of hyperplastic polyps <10mm and subjects with no index lesion. or tissue removed for analysis during colonoscopy.

Sites will submit the colonoscopy reports for all subjects. Subjects who have lesions identified on colonoscopy that are neither biopsied initially nor excised subsequently or that are lost during lesion retrieval and, therefore, not submitted for histopathological analysis, will not be included in the ITS or PP data analysis because they cannot be categorized for the study analysis.

Below is the listing of categories that the central pathologist will use when assessing and determining final categorization. Final categorization will be based on the most significant index lesion. The order of significance is presented below.

1.0: Adenocarcinoma of colorectum, Stage I-IV (Colorectal Cancer, CRC)

2.0 Advanced Adenoma (AA)

2.1: Adenoma with HGD/CIS, any size

2.2: Adenoma with villous growth pattern ( $\geq 25\%$ ), any size

2.3: Adenoma,  $\geq 10$  mm in size

2.4: Serrated lesion,  $\geq 10$  mm (SSA/SSP/HP)

3.0: Adenoma, non-advanced,  $> 5$ ,  $< 10$  mm in size, 1 or 2 adenomas

4.0: Adenomas, non-advanced,  $\geq 3$  adenomas,  $< 10$  mm in size

5.0: Adenoma, non-advanced,  $\leq 5$  mm in size, 1 or 2 adenomas

6.0: Negative: No colorectal adenocarcinoma: no adenomas or SSA/SSP; no HP  $\geq 10$  mm

6.1 Negative, no colorectal neoplasia upon histopathological review

6.2 No findings on colonoscopy, no biopsy(s) taken

## 2.5 mt-sDNA test (Cologuard)

Exact Sciences Laboratories (ESL) will receive and process all stool samples. Assay results will be recorded as 'Positive', 'Negative', 'Sample Could Not Be Processed', or 'No Result Obtained'. The mt-sDNA (Cologuard) test result will not be provided to investigators for clinical management of

study subjects. All mt-sDNA test results will remain blinded to investigators and study subjects. ESL is blinded to all clinical (colonoscopy and pathology) outcomes.

## 2.6 Analysis Populations

The following database components will be used to determine analysis population inclusion:

- mt-sDNA test (Cologuard) exposure data
- mt-sDNA test (Cologuard) results including compliance
- Colonoscopy, biopsy, and pathology reports
- Safety data.

Each data source will be reviewed by the Contract Research Organization (CRO) with specialized input from Exact Sciences for the mt-sDNA (Cologuard) test samples and reflecting input from appropriate medical, clinical, data management, and statistical personnel.

### 2.6.1 Safety (SS) Population

The safety population is described at the subject level. All subjects attempting to use the mt-sDNA (Cologuard) test kit will be included in the Safety Population. This safety analysis set (SS) will be used for the description of safety.

### 2.6.2 Intent-to-screen (ITS) Population

The ITS population is described at the subject level. A subject may have

- a valid mt-sDNA (Cologuard) test and a reportable colonoscopy, OR
- a valid mt-sDNA (Cologuard) test and a complete colonoscopy, OR
- a usable mt-sDNA (Cologuard) test and a reportable colonoscopy

to be included in the ITS population. The ITS analysis set will be used for assessment of effectiveness.

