## 2 STATISTICAL AND ANALYTICAL PLANS

### 2.1 Study Parameters

- This prospective, cross-sectional, multi-center study will enroll subjects 45-49 years of age at average risk for development of colorectal cancer.
- Cologuard is intended for the qualitative detection of colorectal neoplasia-associated DNA markers and for the presence of occult hemoglobin in human stool.
- A positive Cologuard result may indicate the presence of colorectal cancer or advanced adenoma (AA) and should be followed by diagnostic colonoscopy; Cologuard is intended for adults of either sex, 50 years or older, who are typical average-risk candidates for colorectal cancer (CRC) screening.
- Subjects will be required to complete the mt-sDNA (Cologuard) test followed by a screening colonoscopy.
- Exact Sciences Laboratory will perform the Cologuard test.
- Cologuard results will be recorded as 'positive', 'negative', 'no result obtained' or 'sample could not be processed' for each individual corresponding to a specific stool sample.
- A valid mt-sDNA (Cologuard) test is defined as a result that is recorded as either 'positive' or 'negative.'
- A usable mt-sDNA (Cologuard) test is defined as a result that is recorded as either 'positive' or 'negative' (i.e. valid) and is received within 72 hours of sample collection.
- A colonoscopy must follow a Cologuard test.
- In the event of an additional colonoscopy due to inadequate preparation, the colonoscopy with the most significant findings will be considered the study colonoscopy and will be used as the reference test result in the analysis.
- A reportable colonoscopy is defined as one where the procedure was attempted, and a procedure report is available.
- A complete colonoscopy procedure will be considered and defined as: reaching the cecum (or) reaching the junction between the small and large intestine (in the event the cecum has been resected) or a colonoscopy wherein a CRC or AA was identified regardless of any limiting factors experienced during the colonoscopy.
- A subject is considered to be Per Protocol following a usable mt-sDNA (Cologuard) test and complete colonoscopy
- Subjects who have a colonoscopy following a Cologuard sample collection will be considered completed subjects and the date of completion will be the date that the last colonoscopy was performed.

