### 2.6.3 Per-Protocol (PP) Population

The Per Protocol population is described at the subject level. A subject must have a usable mt-sDNA (Cologuard) test and a complete colonoscopy to be included in the PP population. A subject will be excluded from the PP population if there is a major protocol violation or deviation that would compromise the integrity of effectiveness evaluations.

Population	mt-sDNA Test (Cologuard) Kit Attempted	Valid mt-sDNA Test (Cologuard)	Usable mt-sDNA Test (Cologuard)	Reportable Colonoscopy	Complete Colonoscopy	No Major Protocol Deviations
SS	X					
ITS		X		X		
ITS		X			X	
ITS			X	X		

PP			X		X	X
----	--	--	---	--	---	---

Rules regarding ITS exclusion decisions will be prospectively established prior to database lock.

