## 2.8 Effectiveness Analysis

### 2.8.1 Effectiveness Parameters and Hypotheses

The primary effectiveness endpoint of this study is the specificity to advanced neoplasia of the mt-sDNA (Cologuard) test in the 45-49 age group in an average risk population, using colonoscopy with histopathology (if appropriate) as the reference method. The primary effectiveness analysis requires the one-sided 97.5% confidence lower bound of the specificity of mt-sDNA (Cologuard) test to exceed 85.0%.

Subjects with colonoscopic findings in categories 3-6 will be included in the specificity analysis as disease status negative outcomes for the primary endpoint calculation. Thus, specificity to advanced neoplasia (AN) will be calculated for the primary endpoint evaluation. The colonoscopically 'negative' population (category 6) will include those subjects with a colonoscopy showing no findings of colorectal neoplasia, non-neoplastic disease, and/or hyperplastic polyps  $\leq 1$  cm in diameter.

Subjects with no findings on the colonoscopy, no photographic evidence of cecal intubation and no documentation of cecal intubation in the report, will be excluded from Per Protocol analyses. Subjects found to have occult inflammatory bowel disease (IBD) on colonoscopy will be excluded from all analyses. Subjects with an invalid mt-sDNA (Cologuard) test will be excluded from the ITS and Per Protocol population. All excluded cases will be assessed for bias.

Subjects with colonoscopic/histopathologic findings in category 1 (confirmed colorectal cancer cases) will be considered to have a positive outcome and will be included in the CRC sensitivity calculations. Note:

Due to the low prevalence of CRC in the Age 45-49 group, there will likely be no CRC prospectively enrolled in the study, so no primary endpoints will be designed around CRC sensitivity. CRC sensitivity (if any CRC cases are present) will be analyzed as an exploratory endpoint.

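### The SAP's primary analysis set admits colonoscopies that the protocol excludes from the primary endpoint, while SAP Section 5 declares no change

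*SAP*

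**What the plan says.** **SAP.** Section 2.2 makes ITS the main set: "All effectiveness analyses will be performed using the ITS Population with confirmation in a Per Protocol (PP) Population". Section 2.6.2 gives three routes into ITS. The least demanding is "a valid mt-sDNA (Cologuard) test and a reportable colonoscopy, OR", and Section 2.1 explains the term: "A reportable colonoscopy is defined as one where the procedure was attempted, and a procedure report is available". That definition has no condition on the cecum or on bowel preparation. Section 2.8.1 deals with exams that have no findings and no cecal evidence, and ends: "no documentation of cecal intubation in the report, will be excluded from Per Protocol analyses". Section 2.9.1 drops an exam for lack of a reference result only if it is not reportable.

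Preparation appears in the SAP's colonoscopy rules only where a choice between repeat exams must be made: "In the event of an additional colonoscopy due to inadequate preparation, the colonoscopy with the most significant findings will be considered the study colonoscopy". The PP set needs a complete exam: "A complete colonoscopy procedure will be considered and defined as: reaching the cecum", or the small-large bowel junction if the cecum was resected, or any exam that found colorectal cancer (CRC) or advanced adenoma (AA). Section 2.6.3 adds: "Rules regarding ITS exclusion decisions will be prospectively established prior to database lock". Section 5 says the protocol's planned analysis is unchanged.

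**Protocol.** Section 12.2 calls subjects with no findings and no cecal evidence unevaluable and removes them from every analysis. Section 10.6.1 removes them from the primary and secondary endpoints. Appendix 3 removes negative exams without cecal documentation, and negative exams with poor preparation, from endpoint analyses. It waives both conditions only for categories 1.0 and 2.0. Section 12 allows the SAP to modify the plan but requires an amendment for major changes to the primary endpoint or its analysis.

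**The concern.** Specificity is the only primary endpoint, and its denominator is the set of subjects whom colonoscopy shows to be free of advanced neoplasia. An exam that did not demonstrably reach the cecum, or was done through poor preparation, cannot show that. Under the SAP such an exam with nothing found is counted as disease-negative; under the protocol it is left out. One fixed dataset would therefore give two primary denominators and two estimates.

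The two limbs differ in kind. On cecal evidence the documents conflict outright. On poor preparation the SAP is silent, while its ITS definition, read as written, lets these exams in. A reader relying on Section 5 would not know that either question exists.

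**Working it through.** **1. Compare the rules.**

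| Exam with a valid stool test | Protocol, primary endpoint | SAP, ITS (primary) | SAP, PP |
|---|---|---|---|
| No findings, no cecal evidence of either kind | Out (10.6.1, 12.2, App. 3) | In (2.6.2; 2.8.1 limits the exclusion to PP) | Out |
| Negative, poor preparation, cecum reached | Out (App. 3) | In (no exclusion written) | In if the other PP conditions are met (no exclusion written) |
| CRC or AA found, exam limited | In | In | Limited exam no bar (counts as complete) |

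The PP limit in SAP 2.8.1 does not look like loose drafting. The same paragraph removes occult inflammatory bowel disease from all analyses and invalid stool tests from both ITS and PP. Protocol 10.6 says poor-preparation subjects who will not repeat the exam should be withdrawn, but SAP 2.6.2 has no rule that removes a withdrawn subject who has a valid test and a report.

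**2. Reproduce the plan's figures (Protocol 12.3).** Exact one-sided binomial test, null 85.0%, alternative 92.2%, alpha 0.025:
- n = 225: success needs at least 202 test-negatives; power 92.6%. This is the smallest n from which power stays at or above 90% for every larger n checked (up to 319).
- n = 731: success needs at least 641; power 99.9991%. The Clopper-Pearson 95% interval at 674/731 (92.2%) is 90.0% to 94.0%.
- Enrollment: 731/0.8 = 914.

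All agree with the protocol.

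**3. Size of the effect.** The documents give no rate for these exams. From the documents: 731, AA prevalence 3.92%, and a false-positive rate of 1 - 0.922 = 0.078. Assumed: the exams are a share f = 2-10% of the SAP's primary set; they miss all advanced neoplasia (the upper side); a share s = 30-50% of the missed cases test positive; disease-free subjects in these exams have the same 7.8% false-positive rate.

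- SAP set with 731 protocol-evaluable subjects held fixed: 731/(1 - f) = 746 (f = 0.02) to 812 (f = 0.10), so 15 to 81 extra exams.
- Missed cases: 15 × 0.0392 = 0.6 to 81 × 0.0392 = 3.2.
- Understatement of specificity: f × 0.0392 × (s - 0.078).
  - Low: 0.02 × 0.0392 × (0.30 - 0.078) = 0.017 points.
  - High: 0.10 × 0.0392 × (0.50 - 0.078) = 0.165 points.

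**4. Effect on the 85% criterion.** The smallest counts with a one-sided 97.5% lower bound above 85% are 641/731, 654/746 and 711/812. Power at 92.2% is 99.9991%, 99.9994% and 99.9998%. With n = 812 and specificity lowered by 0.165 points it is 99.9996%.

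**5. Tolerance.** Expected negatives among the 731 are 731 × 0.922 = 674.
- n = 746: 674 exceeds 654, so the test passes even if all 15 extra exams are positive.
- n = 812: 711 - 674 = 37 of the 81 extra exams must be negative, so up to 44 positives (54%) are tolerated. Expected positives: 81 × (0.9608 × 0.078 + 0.0392 × 0.50) = 7.7.

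**The case against.** **ITS is still open.** Section 2.6.3 defers ITS exclusion rules to before database lock, and Section 2.2 counts evaluable subjects: "The enrollment target is 731 non-advanced neoplasia and negative evaluable subjects". Both leave room to restore the protocol's exclusions. But no rule is written, the SAP does not define evaluable or tie it to ITS, and 2.8.1 points the other way on cecal evidence.

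**A broad primary set is defensible and PP confirms it.** This is true for the cecal limb, and Protocol 12 lets the SAP modify the plan. It does not make Section 5 accurate or settle whether an amendment is required. PP also applies a 72-hour usability rule and a deviation rule, so it does not isolate this question, and it states no preparation exclusion.

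**On preparation, silence plus Section 5 may mean that the protocol rule carries over.** That is a fair reading, and it is why this limb is not called a contradiction. The ITS definition taken literally still admits these exams, so the rule needs to be written.

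**Versions.** The SAP history records version 2.0 as clarifying the ITS and PP populations, so the populations were revised openly. The SAP cites protocol version 2.0, and the version of the protocol reviewed here cannot be confirmed. Neither point changes the fact that the two documents as supplied disagree.

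**The size rests on assumptions.** This stands. SAP 2.8.1 speaks of about 731 subjects in total. On that basis 15 to 73 of the 731 would be affected, and removing them without replacement leaves 716 to 658, with power still above 99.99%. If 90% of missed cases tested positive, the shift at f = 10% would be 0.10 × 0.0392 × (0.90 - 0.078) = 0.32 points. The conclusion is the same.

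**Conclusion.** The point holds. On cecal evidence the SAP's primary set contradicts three places in the protocol. On poor preparation the SAP omits a protocol exclusion from both ITS and PP. The statement of no change in SAP Section 5 is wrong for the cecal rule.

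The numerical consequence is minor: specificity understated by about 0.02 to 0.17 points under the stated assumptions (affected share 2-10%, all advanced neoplasia missed, 30-50% of missed cases positive), with no realistic threat to the 85% criterion. The direction is conservative as long as missed cases test positive more often than 7.8%. This should be fixed because the primary denominator must be the same in both documents, not because the trial's decision is at risk. Confidence in the textual finding is high; the size depends on rates that the documents do not give.

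**What to change.** 1. In SAP 2.6.2 and 2.8.1, exclude from the primary specificity analysis (a) no-findings or negative exams without cecal evidence and (b) negative exams with poor preparation. State (b) for PP as well. Keep subjects with CRC or AA regardless of exam quality, as both documents already do.
2. Write these as ITS rules now instead of leaving them to the deferred rules in 2.6.3.
3. Report the reportable-colonoscopy set as a sensitivity analysis, and correct Section 5.
4. If the sponsor prefers to keep the reportable set as primary, declare it in Section 5 and decide whether Protocol 12 requires an amendment.
5. In the same edit, reconcile Protocol 10.6.1, which joins the two kinds of cecal evidence with *or*, with 12.2, which uses *and*.
6. Define *negative* and *no findings* so that categories 6.1 and 3-5 are clearly inside or outside each exclusion. At present Protocol 12.2 uses *negative* for category 6, 12.3.1 uses it for all 731 subjects, and Appendix 3 waives the conditions only for categories 1.0 and 2.0.

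The cost is SAP wording plus small protocol corrections. Cecal documentation and preparation quality are already recorded. Some subjects would leave the primary set, partly or wholly offset by the replacement that Protocol 9.4 and 10.6 allow toward the target of 731.

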### 2.6.3 Per-Protocol (PP) Population

The Per Protocol population is described at the subject level. A subject must have a usable mt-sDNA (Cologuard) test and a complete colonoscopy to be included in the PP population. A subject will be excluded from the PP population if there is a major protocol violation or deviation that would compromise the integrity of effectiveness evaluations.

Population	mt-sDNA Test (Cologuard) Kit Attempted	Valid mt-sDNA Test (Cologuard)	Usable mt-sDNA Test (Cologuard)	Reportable Colonoscopy	Complete Colonoscopy	No Major Protocol Deviations
SS	X					
ITS		X		X		
ITS		X			X	
ITS			X	X		

PP			X		X	X
----	--	--	---	--	---	---

Rules regarding ITS exclusion decisions will be prospectively established prior to database lock.

## 2.7 Subject Disposition

All enrolled subjects will be included in summaries of disposition and evaluation for analysis sets. Accounting will be provided for the following parameters:

1. Number of subjects enrolled
2. Number of subjects with a mt-sDNA test (Cologuard).
3. Number of subjects with a complete colonoscopy.
4. Number of subjects with available colonoscopy findings.
5. Study completion status and reasons for discontinuation.

Subject exclusions from analysis sets and associated reasons will be tabulated.

### 2.7.1 Demographic and Other Baseline Characteristics

Gender, age, race, ethnicity, and smoking status will be presented using descriptive statistics by sites and by category for the overall ITS and PP populations. Results will also be presented to show inter-relationships between lesion location, lesion size, ethnicity, and gender.

